9.3.3 Secondary Analyses

To analyze patient reported pain severity using the BPI-sf, we will calculate the "worst pain" i.e., the arithmetic mean of the four severity items to measure pain severity. We will model the difference in "worst pain" from baseline to 15 minutes at each radiation simulation and fractionation visit; with a fixed intercept term for time and a subject level random intercept to account for within-patient variability. We will provide descriptive statistics overall and for each treatment day (mean/standard deviation and frequency distributions of "worst pain").

9.3.4 Exploratory Analyses

Our exploratory aim will assess the impact of Lazanda on treatment delivery efficiency. This will be assessed by comparing treatment delivery efficiency in the Lazanda treated patients to the historic average. To assess this we will quantify each subjects average total time on the treatment table (averaged across each subjects fractionation visits, in minutes). This average will be compared to the clinic's historic average of 6 minutes using a one-sample t-test of the null hypothesis that the average time on the treatment table for Lazanda study patients equals 6 minutes.

We will also consider the effects of baseline pain intensity score, 24-hour opioid use (oral morphine equivalents) and total treatment time at each fraction (minutes) on the change in pain intensity by including each of them as fixed effects in the linear mixed-effects models for PID₁₅. The use of continuous assessment for each individual participant strengthens the validity of the research.²⁰ Our final case series report will assess the overall effect of the study drug on the participant radiotherapy related pain as determined by NRS-11 scores, BPI-sf results, and AEs.

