1.1.2. Radiation Therapy

Radiation therapy, also called radiotherapy, X-ray therapy or irradiation, uses high doses of radiation energy to destroy or damage cancer cells. Radiation breaks down DNA inside cancer cells, reducing cell growth by restricting cell division. Although surrounding normal cells may be affected by radiation, most healthy cells recover and resume their regular functions. Unlike chemotherapy, which exposes the entire body to cancer-directed therapy, radiation therapy is a localized treatment. Radiation therapy is a common treatment for many types of cancer.

There are two main types of radiation therapy: external beam radiation therapy and internal beam therapy (brachytherapy). External beam radiation therapy is the most widely used type of radiation therapy, and can be used to treat large areas of the body. Palliative radiation therapy is typically delivered using 3-dimensional conformal radiotherapy (3DCRT) to direct radiation therapy towards at tumors while minimizing exposure to sensitive normal structures near the tumor in order to avoid treatment-related side effects. **Palliative radiation treatments average 6 minutes, usually last 15 minutes or less, and are completed once a day, five days a week, up to 10 days in duration.**

Advanced cancer patients often require palliative radiotherapy to treat cancer-related symptoms. A total dose of safe and effective radiotherapy is determined quantified in centigray (cGy) and this total dose is delivered over several treatments called *fractions*. Palliative radiation therapy regimens are typically delivered in daily doses of 300-800 cGy per day. This approach

is also known as hypofractionation. Precise delivery of radiation requires patients to lie still on a hard, flat surface that can result in significant acute pain, especially in the setting of painful bone metastases.

[figure not shown]

Figure 1: Pain spinal metastases on CT scan.

Figure 2: Patient in recumbent position during radiation therapy

Radiation Oncology at UCSD

UCSD Moores Cancer Center offers a comprehensive radiation oncology center with advanced radiation therapy services available, including:

- External beam radiation, which 3DCRT, intensity-modulated radiation therapy, image-guide radiation therapy, and volumetric-modulated arc therapy
- Stereotactic radiosurgery (SRS) and stereotactic body radiation therapy (SBRT)
- Brachytherapy (internal radiation therapy)
- Proton therapy

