2.3 Exploratory Objectives

1. To assess the impact on radiation treatment delivery efficiency. This will be quantified by determining the total radiation treatment time.

2. To examine the effect of baseline pain intensity score, 24-hour opioid use (oral morphine equivalents) and total treatment time at each fraction (minutes) on change in pain intensity (PID₁₅)

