2.4 Endpoints

The primary endpoint on this study is change in positional pain intensity as measured by NRS-11 pain scores (**Appendix C**) (PID₁₅= PI₀- PI₁₅). Change in NRS-11 pain scores will be calculated from the time of laying down on the hard surface (0 minutes) to the 15-minute time point. NRS-11 (at time 0 and time 15) will be collected at the radiation simulation and at each subsequent radiation therapy visit. The rationale for obtaining a PID at 15 minutes, is based on the reported intranasal fentanyl C_{max} of 15-30 min.

Secondary endpoints include pain severity difference as measured by the Brief Pain Inventory Short Form (BPIsf)¹⁸ (**Appendix D**). We will compare the BPIsf pain scores from the time of laying down on the hard surface (0 minutes) to 15 minutes after laying down at each fractionation visit. As a secondary endpoint we will also examine Lazanda safety, defined as the rate of drug-related adverse events experienced assessed according to the NCI's CTCAE v4.03 toxicity criteria.

Exploratory endpoints will include total recumbent time at each fractionation visit, measured in minutes.

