3.2 Exclusion Criteria

Subjects meeting any of the exclusion criteria at baseline will be excluded from study participation.

1. Patient is currently receiving or has received another investigational agent within 30 days or monoamine oxidase inhibitor within 14 days prior to Lazanda administration.
2. Patients who require immobilization with a thermoplastic mask for radiation treatment.
3. Patient is planned to receive interventional procedures (i.e. surgery) that may affect study outcomes.
4. Patient has a history of hypersensitivity to fentanyl or opioids.
5. Patient is pregnant or nursing. There is a potential for congenital abnormalities and for this regimen to harm nursing infants.
6. Patient is being treated with oxymetazoline for allergic rhinitis or has a disorder or current medication use likely to adversely affect normal functioning of the nasal mucosa.
7. Patient has uncontrolled or rapidly escalating background pain.
8. Patient has bradyarrhythmia.
9. Patient is considered medically unstable.
10. Patient is thought to be at risk for misuse, abuse, addiction or overdose for Schedule II controlled substance, as evidenced by the following:
 - a. An Opioid Risk Tool (ORT) score of greater/less than or equal to 8.²
 - b. A review of the California Prescription Control Monitoring Program (PDMP) Controlled Substance Utilization Review and Evaluation System (CURES) report demonstrates multiple prescribing providers and/or multiple pharmacies in the last 30 days. The CURES report will also be used to verify opioid use, opioid dose, and current prescribing providers.

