Secondary objectives will seek to assess patient reported pain severity using the BPI-sf (**Appendix D**), and evaluate adverse effects associated with Lazanda use utilizing the NCI CTCAE version 4.03 before and after palliative radiation.

Exploratory objectives will assess the impact on radiation treatment delivery efficiency, which will be quantified by determining the total time of radiation treatment, defined as the average time on the treatment table for each fractionation visit. A second exploratory objective will be to examine the effect of: baseline pain intensity score, 24-hour opioid use (oral morphine equivalents) and total treatment time at each fraction (minutes) on change in pain intensity (PID15)

After obtaining written informed consent, patients will have the following procedures completed to confirm eligibility: physical exam with vital signs and weight, ECOG performance status, comprehensive metabolic panel, and a serum pregnancy test (women of child-bearing potential only). During this screening period, patients will also complete a baseline NRS pain score and BPI-sf questionnaire (**Appendix D**), and report baseline 24-hour opioid dose.

Event	NRS-11	BPI-sf	Diaries		
			Medication Use	Nausea Vomiting	Laxation
Simulation	T-15, T0, T+15	T15+	X	X	X
Daily radiation fraction	T-15, T0, T+15	T15+	X	X	X

Table 1: Summary of Assessments; NRS-11 = numerical rating scale; BPI-sf = Brief Pain Inventory short form; T-15= 15 minutes prior; T0=at point of laying down; T+15 = 15 minutes after layind down; T15+ = any point after 15 minutes from laying down; X = once daily

Simulation Evaluation

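### The exploratory test of table time against a historic 6 minutes cannot show what Lazanda does to delivery efficiency; report an estimate with a confidence interval instead

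*Combined protocol and SAP*

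**What the plan says.** Section 9.3.4 sets out to assess Lazanda's impact on treatment delivery efficiency. For each subject it takes the "average total time on the treatment table (averaged across each subjects fractionation visits, in minutes") and compares the result with the clinic's historic average, "using a one-sample t-test of the null hypothesis that the average time on the treatment table for Lazanda study patients equals 6 minutes". The Statistical Methodology entry of the Study Summary repeats this plan.

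The only other mention of the figure is background text in Section 1.1.2: "Palliative radiation treatments average 6 minutes, usually last 15 minutes or less". No SD, number of patients, calendar period, source or case mix is given in either place.

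The study-side measure has several names:
- Section 2.3, on the efficiency objective: "This will be quantified by determining the total radiation treatment time".
- Section 2.4, repeated in substance in Section 9.1: "Exploratory endpoints will include total recumbent time at each fractionation visit, measured in minutes".
- Section 4.1, on the total time of radiation treatment: "defined as the average time on the treatment table for each fractionation visit".

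Section 4.1 also has the coordinator record recumbent time, glossed as time lying down, and separately the time in the unit. The analysis does not use time in the unit.

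The Schedule of Events (note 2) and Sections 4.1 and 5.1.11.1 require an NRS pain score 15 minutes after the patient lies down (T+15).

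**The concern.** A one-sample t-test asks only whether the study mean differs from a fixed number. To read the answer as an effect of Lazanda, that number must be what these patients' table time would have been without the drug, measured over the same interval.

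The documents do not establish this. The figure has no described population, whereas the trial enrols opioid-tolerant patients with symptomatic bone metastases and excludes "Patients who require immobilization with a thermoplastic mask for radiation treatment". Nor is there an internal check: Lazanda is given at simulation and before every fraction, and the Schedule of Events records recumbent time only at those visits. The Appendix I log has a row for a mock or baseline visit, but for pain scores only.

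The T+15 score raises a further problem. It falls 15 - 6 = 9 minutes past the benchmark. If patients remain on the table for it, the protocol itself lengthens the measured time.

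At stake is a p-value that could be reported as evidence that Lazanda speeds or slows treatment when it reflects something else.

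**Working it through.** **Inputs from the documents.** Benchmark 6 minutes (9.3.4). Enrolment of about 6 with 10% dropout and an analytic n of 5 (Study Summary): 6 × 0.90 = 5.4, rounded down to 5, which reproduces the plan's figure. Section 4.1 and the accrual table instead give 15, so n = 15 is also shown.

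**Assumptions.** The documents give no SD, alpha or sidedness for this test. I take a two-sided 5% level and a between-patient SD of 2, 3 or 4 minutes. The SD of 1.48 in Section 9.2 concerns pain-score change and does not apply.

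**Step 1: rejection from a mismatch alone.** If the appropriate reference differs from 6 minutes by d and the drug has no effect, the test statistic is noncentral t on n - 1 degrees of freedom with noncentrality d√n/SD. For n = 5, d = 2 and SD = 2, the noncentrality is 2 × 2.236/2 = 2.236 and the critical value is 2.776. The rejection probability is 0.401.

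| n | Shift d | SD 2 | SD 3 | SD 4 |
|---|---|---|---|---|
| 5 | 2 min | 40.1% | 21.1% | 14.1% |
| 5 | 4 min | 90.9% | 61.4% | 40.1% |
| 6 | 2 min | 50.7% | 26.5% | 17.1% |
| 15 | 2 min | 94.9% | 67.1% | 43.8% |

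More patients make a false attribution more likely, because the mismatch does not shrink with n.

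**Step 2: the T+15 score.** If patients stay down until it is taken, mean recumbent time is about 15 minutes and d = 9. At n = 5 the test rejects in 100%, 99.8% and 95.7% of trials for SD 2, 3 and 4, always toward longer time. At n = 6 and SD 4 it rejects in 99.0%.

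**Step 3: non-rejection.** At n = 5, 80% power needs a difference of 1.68 SD. At SD 2 that is 1.68 × 2 = 3.4 minutes on a 6-minute base. A true 2-minute saving offset by a 2-minute case-mix excess leaves a net difference of zero, which is rejected only 5% of the time.

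**Step 4: the benchmark as an exact constant.** If the 6 minutes was itself a mean of n₀ patients with the same SD, the true type I error at n = 5 is P(|t₄| > 2.776/√(1 + 5/n₀)).

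| n₀ | √(1 + 5/n₀) | Type I error |
|---|---|---|
| 10 | 1.225 | 8.6% |
| 20 | 1.118 | 6.8% |
| 50 | 1.049 | 5.7% |
| 100 | 1.025 | 5.4% |

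**Step 5: precision of an estimate.** The 95% half-width at n = 5 is 2.776/√5 = 1.24 SD, or 2.5 to 5.0 minutes for SD 2 to 4.

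**The case against.** The strongest reply is that the plan does compare like with like. Section 4.1 defines radiation treatment time as table time and glosses recumbent time as time lying down, so the three labels can be read as one quantity. In 9.3.4 the historic average follows directly on the definition of table time. A reader might infer that the 6 minutes is known to be a different interval, for instance one without set-up. The documents do not support that. But these definitions concern the study patients; nothing says how the historic figure was timed.

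A reader might also infer that the historic patients are known to differ. They are not described, and the general phrase about palliative treatments is background text. Comparability is unaddressed, not disproved.

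Nor do the documents say that patients stay down until T+15. Section 1.1.2 says treatments usually last 15 minutes or less, so the score may often be taken after they get up. Step 2 is therefore conditional.

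The shifts, SDs and historic sample sizes are assumptions, and the constant-benchmark error is small unless n₀ was small. The wide interval comes from the sample size and would remain under the fix.

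Finally, the analysis is exploratory in a case series, and the closing sentence of 9.3.4 rests the final report on pain scores and adverse events, not on efficiency. That limits the importance of the point. It does not make the p-value interpretable, and 9.3.4 still presents the test as assessing Lazanda's impact.

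**Conclusion.** The point holds as one of attribution. With a benchmark of undescribed origin and no untreated table time in the trial, neither outcome of this test can be credited to Lazanda. Under the assumed SDs of 2 to 4 minutes, a 2-minute mismatch alone rejects in 14 to 40% of trials at n = 5. If patients remain recumbent for the T+15 score, rejection toward longer time occurs in about 96% or more, for SDs up to 4 minutes. Treating the benchmark as exact is a lesser issue, with type I error of 5.4 to 8.6% for an assumed historic n of 100 down to 10.

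It would go too far to say that a mismatch has been shown, or that nothing can be said about table time: a descriptive estimate remains sound. The primary endpoint is untouched, so this is a low-severity improvement.

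**What to change.** 1. Use one named interval, with start and stop points, in the Study Summary (Objectives and Statistical Methodology) and Sections 2.3, 2.4, 4.1, 9.1 and 9.3.4. The stop point should exclude any time spent on the table only for the T+15 score.
2. Report the mean of patient means with its 95% CI as a descriptive result, and drop the test against 6 minutes. This fits the case-series reporting described in Section 10.13.
3. Compare with a historic figure only if it covers the same interval in comparable patients and comes with its SD and n. Use a two-sample method, and do not attribute a difference to Lazanda.

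The cost is one exploratory p-value and a wording amendment, which Section 10.10 sends to the IRB. Recumbent time is already recorded; if the current record runs on to the T+15 score, its stop time needs redefining. A query of clinic records is needed only if the historic comparison is kept.

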10.0 STUDY MANAGEMENT

10.1 Conflict of Interest

Any investigator who has a conflict of interest with this study (patent ownership, royalties, or financial gain greater than the minimum allowable by their institution, etc.) must have the conflict reviewed according to UCSD conflict of interest policy.

10.2 Institutional Review Board (IRB) Approval and Consent

The IRB should approve the consent form and protocol prior to any study-related activities. It is expected that the IRB will have the proper representation and function in accordance with federally mandated regulations.

In obtaining and documenting informed consent, the investigator should comply with the applicable regulatory requirement(s), and should adhere to Good Clinical Practice (GCP) and to ethical principles that have their origin in the Declaration of Helsinki.

Before recruitment and enrollment onto this study, the patient will be given a full explanation of the study and will be given the opportunity to review the consent form. Each consent form must include all the relevant elements currently required by the FDA Regulations and local or state regulations. Once this essential information has been provided to the patient and the investigator is assured that the patient understands the implications of participating in the study, the patient will be asked to give consent to participate in the study by signing an IRB-approved consent form.

Prior to a patient's participation in the trial, the written informed consent form should be signed and personally dated by the patient and by the person who conducted the informed consent discussion.

10.3 Registration Procedures

All patients must be registered with the UCSD Moores Cancer Center Clinical Trials Office before enrollment to study. Prior to registration, eligibility criteria must be confirmed and an eligibility checklist completed. Once eligibility is confirmed, patient will be given a unique sequential study number.

10.4 Data Collection and Management

Records and data to be obtained from the study subjects are detailed above in the Schedule of Events. Subject outcome information will be documented in the electronic medical record and subject's research record. Data for this study will be entered into a password-protected set of electronic case report forms via the Velos eResearch web-based system. Velos eResearch is an integrated software system for managing clinical trials. This system supports several clinical trial functions, including electronic case report forms, tracking and scheduling of subject visits and events, and study reporting. The software links to the UCSD Health System's Epic Electronic Medical Record System to provide improved information and integration for clinical research projects. A robust support team assists investigators in implementing protocols and calendars and building electronic case report forms. Velos provides automated data export procedures for designated users into Excel, and then transferred into SAS and R. Access to the Velos database for this study will be limited to those users required to perform study-specific functions such as data entry and monitoring. A designated study coordinator from the UCSD Moores Cancer Center Clinical Trials Office will be responsible for entering all study data.

10.5 Subject Data Protection

In accordance with the Health Information Portability and Accountability Act (HIPAA), subjects who have provided written informed consent must also sign a subject authorization to release medical information to the study Sponsor and allow a regulatory authority, or Institutional Review Board access to subject's medical information relevant to the study.

10.6 Data and Safety Monitoring/Auditing

In addition to adverse event monitoring and clinical oversight by the principal investigator and co-investigators, quality assurance of the study will be performed by a UCSD Moores Cancer Center Clinical Trials Office internal monitor. Monitoring intervals will be dependent upon the rate of enrollment, and are anticipated to occur approximately every 3-4 months.

This study will also use the UCSD Moores Cancer Center DSMB to provide oversight in the event that this treatment approach leads to unforeseen toxicities. Data from this study will be reported every 6 months and will include

- 1) the protocol title, IRB protocol number, and the activation date of the study.
- 2) the number of patients enrolled to date
- 3) the dates of patient enrollment
- 4) a summary of all adverse events regardless of grade and attribution
- 5) outcome data for evaluable patients when available
- 6) a summary of any recent literature that may affect the ethics of the study.

It will be left to the Investigator's clinical judgment whether or not an adverse event is related and of sufficient severity to require the subject's removal from treatment. Subsequent review of serious, unexpected and related adverse events by the principal investigator, DSMB, UCSD and/or HRPP, may also result in suspension of further trial interventions/ administration of study drug at a site. The principal investigator retains the authority to suspend additional enrollment for the entire study as applicable.

10.7 Adherence to the Protocol

Except for an emergency situation in which proper care for the protection, safety, and well-being of the study patient requires alternative treatment, investigators are required to conduct their research according to the plans reviewed and approved by the IRB.

10.8 Emergency Modifications

Investigators may implement a deviation from, or a change of, the protocol to eliminate apparent immediate hazards/risks to trial subjects without prior IRB approval. Any such emergency modification implemented must be noted and reported to the IRB along the lines of a protocol deviation or violation, depending on the nature of the modification.

10.9 Protocol Violations

Any unplanned variance from an IRB approved protocol is considered a violation and must be reported to the IRB in a timely fashion.

- A) Major violations must be reported to the IRB within 10 working days of awareness of the violation. Major violations include:
- Instances that have harmed or increased the risk of harm to one or more research participants.
 - Instances that have damaged the scientific integrity of the data collected for the study.
 - Results from willful or knowing misconduct on the part of the investigator(s).
 - Demonstrates serious or continuing noncompliance with federal regulations, State laws, or University policies.
- B) Minor violations may be reported to the IRB at the time of the continuing review. Minor violations have no substantive effect on the risks to participants or on the scientific integrity of the research plan or the value of the data collected.

